2. OBJECTIVES AND HYPOTHESES

2.1 Primary Objective(s) & Hypothesis(es)

This study has been divided in two steps where step 1 has assessed the study population length and follow up as well as comparability between SGLT-2i users and users of other diabetes medication groups. The objectives of step 1 are described in the full protocol (D1690R00015). This amendment concerns step 2 which is a comparative analysis of the risk for CV events between SGLT-2i users and a group of active comparators.

Step 2 has one primary, one secondary and two exploratory objectives and will only be conducted given that a comparative analysis is feasible based on the results from step 1. Feasibility was determined by the following requirements a) the study population has enough length of follow up, required variables of interest, and size to have sufficient power to assess the outcome of interest according to the power calculations presented in Section 5.3 and b) a suitable comparator group. Suitability of comparator groups was assessed based on the propensity score matching by applying normal requirements to assess sufficient match between different groups. This process will be outlined in more detail in the statistical analysis plan (SAP). Step 1 also informed whether analysis needed to be done on SGLT-2i class level or dapagliflozin separately applying the above-mentioned criteria. As step 2 is considered feasible based on the criteria, this protocol amendment outlines the analysis including the specifics about the treatment group, comparator group, and primary outcome, for this step. The primary, secondary and explorative objectives of the study amendment (step 2) are:

Primary objective

To compare the risk for hospitalization for heart failure between patients with T2DM who are new users of SGLT-2 inhibitors as a class versus an active comparison group including patients with T2DM who are new users of other GLD.

Secondary objective

To compare all-cause mortality between patients with T2DM who are new users of SGLT-2 inhibitors as a class versus an active comparison group including patients with T2DM who are new users of other GLD. Due to data availability this objective can only be addressed in UK and the Nordic countries.

Exploratory objectives

To estimate the incidence of acute myocardial infarction and atrial fibrillation respectively in new users of SGLT2 inhibitors and of other GLD.

3. METHODOLOGY

3.1 Study Design – General Aspects

This is a cohort study of patients with T2DM who are new users of SGLT-2 inhibitors and other GLD, respectively, in the US, UK, Sweden, Denmark, Norway, Germany and Canada. Additional countries contributing with corresponding data fulfilling the

requirements for the objectives of the study as described in the main protocol (D1690R00015) may be added in a second phase of this study.

The study period will range from launch of the first SGLT-2i in each of the countries (November 2012 for Nordics, Germany and UK, March 2013 for US, and January 2015 in Canada) and end at latest available data in each data source.

A new user of SGLT-2i, or another diabetes medication, is defined as an individual receiving a prescription or filling a prescription of the mentioned diabetes medication classes with no issued/dispensed prescriptions of that medicine class during the preceding year.

The date of the first issued /filled prescription of the SGLT-2i and other GLD (index medication group) during the study period will be denoted the *index date*. For the other GLD group consisting of all other diabetes medications except SGLT-2 inhibitors the first initiation of a new diabetes medication class will be the index date for those initiating only one treatment episode in this group during the study period. For patients in this group initiating two or more diabetes medication classes during the study period, one of the episodes will be randomly selected and the first day of that episode will be the index date for that patient. Patients will be followed from index date (excluding) to the earliest of end of use of the index medication group, migration/leaving the practice/leaving the database, last date of data collection, death date or date of outcome. The availability of some of this information differs between databases.

Baseline characteristics including demographic and clinical characteristics will be captured for patients before the index date (including).

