3.2 Study Population

New users will be defined as individuals with T2DM either receiving or filling a prescription of a SGLT-2i or other GLD during the study period. The other GLD comparator group will include all diabetes medicines, allowing combinations and monotherapy use with the exception of SGLT-2i. Comparators will be matched on baseline characteristics for up to a 1:3 ratio for each SGLT-2i user.

The class SGLT-2i include dapagliflozin, canagliflozin and empagliflozin. Individuals with a previous issued/filled prescription of that medicine class during the preceding year (i.e. 365 before the index date) are not regarded as new users.

The date of the first issued /filled prescription of the SGLT-2i and other GLD classes (index medication group) during the study period will be denoted the *index date*. For the group consisting of all other diabetes medications except SGLT-2 inhibitors the first initiation of a new diabetes medication class will be the index date for those in this group initiating only one treatment episode during the study period. For patients in this group initiating two or more diabetes medication classes during the study period, one of the episodes will be randomly selected and the first day of that episode will be the index date for that patient.

A history of CV event is defined as a diagnosis of MI, unstable angina, stroke, heart failure, TIA, coronary revascularization (CABG or PCI) or occlusive peripheral artery disease before the index date. ICD-codes for these are provided in Table 8.1 in section 8 in the full protocol (D1690R00015). Other CV risk factors that also will be assessed but not included in the definition of history of CV events include obesity, dyslipidemias (hypercholesterolemia), hypertension, end stage renal disease and low socioeconomic status. These will be assessed where possible.

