3.4 Exclusion Criteria

Exclusion criteria are:

- Patients with a T1DM diagnosis (ICD9 codes 250.x1, 250.X3 or ICD 10 codes E10 and O24.0, read codes for T1DM are presented in the full protocol (D1690R00015) Table 8.2) at any time

- Patients with gestational diabetes (ICD9 codes 648.8; ICD10: O24.4; read codes L180811 and L180900) within 1 year before index date

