4. VARIABLES AND EPIDEMIOLOGICAL MEASUREMENTS

4.1 Exposures

The exposure of interest is use of SGLT-2 inhibitors (dapagliflozin, canagliflozin and empagliflozin) or other GFLD including all diabetes medications except initiation of SGLT-2 inhibitors. An individual will be defined as a user on the index therapy for the duration of subsequent prescriptions. A 100 % of previous number of days' supply will be added after the last day of supply. If there is no refill within this period the patient is censored at the last day of the grace period. An individual will only be included if he or she is a new user of one of the mentioned medicine groups. Insulin use in the three months preceding index date will be assessed and descriptions of characteristics will be conducted by insulin use before index date.

An individual will be considered exposed to the medication of interest from the index date and until the last day with medication available (either last day of the last filled prescription (Sweden, Norway, Denmark, Germany, Humedica, MarketScan, Canada's MCHP) or last day of the last issued prescription (CPRD and THIN) plus a grace period of the number of day's supply contained in the last filled or issued prescription.

The SGLT-2i class is defined as the medications dapagliflozin (ATC code A10BX09, A10BD15), canagliflozin (A10BX11, A10BD16) and empagliflozin (A10BX12, A10BD19). DPP-4i includes all available medicines in the ATC category A10BH and the substances A10BD07,08,10,11,13,18 (combinations with metformin). The group other diabetes medications include all diabetes medications in A10A and A10B except SGLT-2 inhibitors. Brand names used in the US of the medication groups are outlined in Table 8.3 in section 8 appendix in the full protocol (D1690R00015).

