5.2.3 Strengths and Limitations

- This study will include data from multiple countries in order to increase the power of the analyses
- Because of the real world observational data, the population of this study will be more diverse compared to a randomized controlled trial and the results of this study will be more generalizable to a broader diabetes population.
- This study will provide some insight on the potential cardiovascular benefits of SGLT-2i/dapagliflozin ahead of the DECLARE study results.
- The set of core outcomes and variables will be limited to ensure as large as possible population
- The data in selected (to be selected) databases reflects everyday health care and is collected for non-research purposes. Therefore, clinical values are captured as part of routine clinical practice and there is considerable variation in the timing and completeness of measurements
- Some databases reports issued prescriptions only. In these cases, no information may be available as to whether the patient collected the prescription and used the product. However, if a product is repeatedly issued this most likely indicates that the medication is used.
- The index prescription i.e. the first prescription of a SGLT-2i medicine may not be the first ever SGLT-2i prescription for the patient in GP based EMR databases. For example, the first prescription may have been initiated by a consultant but then the

general practitioner will usually continue the care which could be a scenario in databases like CPRD and THIN.

- Will not be possible to define the outcome exactly equivalent to EMPA-REG as the databases will most likely not have all the required tests recorded
- Comparators will likely have earlier index dates to larger extent than SGLT-2i users and thus may have longer follow up
- Combination use of several of the classes of interest or a history of use of several of the classes of interest will occur and a classification of this will be assessed
- Patients may have limited persistence with their SGLT-2i treatment
- Cannot interpret statistical analyses from this study in the same way as could be done with a randomized clinical trial because this is an observational study
- The 1:3 treatment allocation ratio of SGLT-2i:other GLD patients may reduce the representativeness of the SGLT-2i patients selected for this study compared to the overall SGLT-2i patient population

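### As written, a current or recent SGLT-2i user who starts another glucose-lowering class is not barred from the comparator arm, and no rule handles a patient who qualifies for both arms

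*Combined protocol and SAP*

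**What the plan says.** - **New-user rule.** Section 3.1 gives one definition for SGLT-2i and for other diabetes drugs: a patient receiving or filling a prescription "with no issued/dispensed prescriptions of that medicine class during the preceding year".
- **Look-back in Section 3.2.** "Individuals with a previous issued/filled prescription of that medicine class during the preceding year" are not regarded as new users. This comes directly after the sentence listing the drugs in the SGLT-2i class.
- **Comparator in Section 3.2.** It takes in all diabetes medicines, "allowing combinations and monotherapy use with the exception of SGLT-2i".
- **Comparator in Section 4.1.** The exposure is described as "including all diabetes medications except initiation of SGLT-2 inhibitors". Later in the section the definition is by drug code: "The group other diabetes medications include all diabetes medications in A10A and A10B except SGLT-2 inhibitors".
- **Exclusions.** Section 3.4 lists two: type 1 diabetes, and "Patients with gestational diabetes (ICD9 codes 648.8; ICD10: O24.4; read codes L180811 and L180900) within 1 year before index date". Neither it nor Section 3.3 addresses SGLT-2i use at or before a comparator index date.
- **Several episodes.** Section 3.1, on the other-GLD group: "For patients in this group initiating two or more diabetes medication classes during the study period, one of the episodes will be randomly selected". Section 3.2 repeats the rule.
- **Acknowledged limitation.** Section 5.2.3 expects that combination use or "a history of use of several of the classes of interest will occur and a classification of this will be assessed".

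**The concern.** The primary and secondary objectives (Section 2.1) contrast SGLT-2i with other glucose-lowering drugs. That contrast needs a comparator arm free of SGLT-2i at time zero. Under a washout specific to the class being started, a patient on SGLT-2i can meet the comparator definition and be followed as a control while taking the test drug from day one. As-treated handling (Section 5.1.1) concerns additions and switches after index, so it does not reach exposure already present at entry.

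The same patient may already have been counted in the SGLT-2i arm. The plan has no rule that makes the arms mutually exclusive and none for the dependence that dual membership creates. Section 6.1.1 has different groups analysing different databases, so an ambiguous entry rule could be coded differently by country before the estimates are pooled.

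**Working it through.** **1. Patients traced through the stated rules**

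- *Starts an SGLT-2i in 2014 and adds a GLP-1ra or insulin in 2015 while still taking it.* Section 3.1: a new user of the added class. Section 3.4: not excluded. Section 4.1: the event is not the initiation of an SGLT-2i, and the new drug falls in the other-GLD code group. Section 3.2: barred if the class in the look-back sentence means SGLT-2i, admitted if it means the class being started. The same patient is also an SGLT-2i new user from 2014.
- *Stopped an SGLT-2i a few months before starting another class.* Same result.
- *Starts both classes on one day.* Meets both new-user definitions. The look-back covers the year before the index date, so it does not reach this case, and no sentence assigns an arm.
- *Starts a DPP-4i first and an SGLT-2i later.* Has a valid index date in each arm. Random episode selection works only among other-GLD episodes, so it does not choose between arms.

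**2. The plan's own figures (Section 5.3)**

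Inputs: HR 0.80, two-sided alpha 0.05, 85% power, 1:3 allocation, 970 events, rates 0.5 and 0.625 per 100 person-years.

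- Schoenfeld events: (1.960 + 1.036)² / [0.25 × 0.75 × (ln 0.80)²] = 962, close to the stated 970.
- Power at 970 events: Φ(√(970 × 0.1875) × 0.2231 − 1.960) = Φ(1.049) = 85.3%.
- Person-years: 970 / (0.005 + 3 × 0.00625) = 40,842 for SGLT-2i, and three times that is 122,526 for control. Both match.

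**3. Dilution alone**

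Let f be the share of comparator person-time on SGLT-2i. The documents give no value, so f is assumed. Background risk is taken as equal and the drug effect as constant:

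HR(f) = 0.5 / [0.625(1 − f) + 0.5f] = 0.80 / (1 − 0.2f)

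| f (assumed) | HR | Power at 970 events |
|---|---|---|
| 0 | 0.800 | 85.3% |
| 1% | 0.802 | 84.7% |
| 2% | 0.803 | 84.0% |
| 5% | 0.808 | 82.0% |
| 10% | 0.816 | 78.1% |
| 20% | 0.833 | 69.1% |

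Events needed for 85% power at 5%, 10% and 20% are 1,055, 1,163 and 1,441.

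**4. The opposing force**

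Suppose SGLT-2i-exposed comparators, being patients whose therapy was intensified or changed, have r times the background risk of the other comparators. The control rate becomes 0.625(1 − f) + 0.5rf. It stays at 0.625 when 0.5r = 0.625, that is r = 1.25. Below 1.25 the HR moves towards 1. Above 1.25 it moves below 0.80. The documents do not give r.

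**The case against.** The strongest reply is that Section 3.2 already bars these patients. Its look-back sentence follows a sentence naming only the SGLT-2i class, so in place it can mean that anyone with SGLT-2i in the prior year is not a new user of anything. The phrase "allowing combinations and monotherapy use with the exception of SGLT-2i" can likewise be read as ruling out combinations with SGLT-2i. Both readings are fair. They conflict, however, with the generic definition in Section 3.1 and with the word initiation in Section 4.1. They also leave dual eligibility at different dates open, and they say nothing explicit about which arm takes a same-day start.

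Second, matching might remove the problem. Section 5.1.1 calls for all observed variables that may affect treatment or outcome. A reader might infer that prior SGLT-2i use could never be handled this way because it is zero in the SGLT-2i arm. That goes too far: if it were entered, the separation would give such comparators scores near zero, and the caliper would tend to leave them unmatched. But the listed variables do not name it, and an exclusion that works only through the score should be written as an exclusion.

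Third, the share may be small. Section 1.1 describes limited exposure to the class and mainly third-line use. Section 5.2.3 expects limited persistence and earlier comparator index dates. At 1% to 2% the effect is negligible. This point stands.

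Fourth, the full protocol (D1690R00015) and a separate SAP are cited but not available here, and either might hold a further rule. Section 2.1 nevertheless says that this amendment sets out the treatment and comparator groups for step 2, so the rule belongs here.

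**Conclusion.** The gap holds. Sections 3.1, 3.4 and 4.1 do not bar a current or recent SGLT-2i user from the comparator arm. Section 3.2 can be read the other way, so the text must be reconciled. No rule on any reading handles same-day starts or eligibility for both arms at different times.

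Three stronger readings are tempting, and the documents do not support them:

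- *That the plan does place SGLT-2i users in the comparator arm.* The text fails to bar them. Whether they enter depends on which section a programmer follows.
- *That the HR is necessarily biased towards 1.* Dilution acts that way, but intensified patients may carry higher risk. With r above 1.25 the net movement reverses.
- *That power is materially lost.* The fall from 85.3% to between 84.7% and 69.1% rests on assumed shares of 1% to 20%, equal background risk and a constant HR.

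Appearing in both arms at different times is not in itself an error in a new-user design. What is missing is a rule for assignment or for the dependence. The point still merits correction before analysis, because it concerns who is in the primary contrast and can be settled with prescription data already used for the washout.

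**What to change.** Reconcile Sections 3.1, 3.2 and 4.1, and state in 3.1, 3.2 and 3.4 that:

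1. An other-GLD index date is eligible only if there is no SGLT-2i prescription, including fixed-dose combinations, on that date or in the preceding 365 days.
2. The random comparator episode is drawn from eligible episodes only.
3. A patient starting both classes on the same day is assigned to the SGLT-2i arm.
4. Comparators are not excluded because they start an SGLT-2i later, since that would condition on the future.
5. A patient eligible for both arms at different times is either assigned to one arm by a rule using only pre-index information, or kept in both with patient-clustered standard errors.

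The 970-event target need not change. The cost is a few lines of text, one filter on prescription records already held, and the loss of some comparator patients. The documents do not give that number, so each database should report it.

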4.3 Other Variables and Covariates

Covariates will be measured to describe baseline characteristics of the study population. A set of core covariates will be determined where data is available in all databases and is described in the full protocol (D1690R00015). Additional covariates will be described

where available in specific databases. Baseline covariates will be measured prior to the index date (including) (age will be on index date) and by clinical coding from either primary or secondary care records. Therapies at baseline will be assessed in the twelve months before and on the index date except for diabetes medication at baseline. Diabetes medication at baseline will be assessed in the twelve months before the index date (excluding).

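### Restarters of older glucose-lowering classes can enter the comparator arm as new users, and the 12-month drug-history covariate cannot identify them

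*Combined protocol and SAP*

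**What the plan says.** One washout rule serves both arms. Section 3.1 requires that a new user be someone "with no issued/dispensed prescriptions of that medicine class during the preceding year", and Section 3.2 repeats it: "Individuals with a previous issued/filled prescription of that medicine class during the preceding year" do not count as new users, the year being taken as 365 days.

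The calendar frame is set by the test drug. In Section 3.1, "The study period will range from launch of the first SGLT-2i in each of the countries", and the index date is "The date of the first issued /filled prescription of the SGLT-2i and other GLD (index medication group) during the study period". For comparators who start two or more classes in that period, "one of the episodes will be randomly selected and the first day of that episode will be the index date for that patient".

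The comparator group is broad. Section 4.1 states: "The group other diabetes medications include all diabetes medications in A10A and A10B except SGLT-2 inhibitors".

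The drug-history covariate has its own window. Section 4.3 states: "Diabetes medication at baseline will be assessed in the twelve months before the index date (excluding"). Section 5.1.1 lists variables to be considered for the propensity score. These include diabetes severity and duration, insulin use (short or long term), an add-on/switch indicator and lookback duration. Section 5.2.3 accepts that patients will have a history of several classes and says this will be classified. It does not say that the classification enters the score.

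**The concern.** A symmetric rule gives different populations in the two arms. On the SGLT-2i side there was nothing to use locally before the study period opened, so the first prescription in the period is nearly always the first ever. On the comparator side the classes include ones in use before that date. A patient who left such a class more than 365 days ago and comes back to it passes the same test.

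The comparison is then between near-pure first-time initiators and a mixture of first-time initiators and restarters. Restarters may differ in disease stage and in the reason for the prescription. If those differences bear on heart failure risk and remain after matching, they shift the hazard ratio. The covariate most likely to reveal a restart has the same 12-month span as the washout, so it cannot do so.

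**Working it through.** **The plan's own figure.** The event target reproduces and does not depend on this point. The Schoenfeld formula for hazard ratio 0.80, two-sided alpha 0.05, 85% power and 1:3 allocation gives (1.960 + 1.036)² / [0.25 × 0.75 × (ln 0.80)²] ≈ 962 events, against 970 in Section 5.3. Power at 970 events is 85.3%. The stated exposure gives 40,842 × 0.005 + 122,526 × 0.00625 = 204.2 + 765.8 = 970.0 events.

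**Can a restarter enter?** Take a patient who used a sulfonylurea, stopped it 13 months ago and restarts it within the study period.

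1. Sections 3.1 and 3.2: no sulfonylurea in the preceding 365 days, so the patient is a new user of that class.
2. Section 4.1: the class belongs to the comparator group.
3. Sections 3.3 and 3.4: no inclusion or exclusion criterion concerns earlier use of the index class.
4. Section 3.1, multiple initiations: the random choice of episode does not favour first-ever starts, so it does not remove restarts.
5. Section 4.3: the 12-month window shows no sulfonylurea, exactly as for a first-time starter. Anyone who passes the washout has a blank for the index class in this covariate.

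**Can the same happen in the SGLT-2i arm?** Only marginally. The period starts at launch and the index is the first prescription in it. The exceptions are the consultant-initiated prescriptions that Section 5.2.3 describes for databases such as CPRD and THIN, and any use before a patient joined a database, since Section 3.3 asks only for more than one year of history.

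**Possible size.** The documents give neither a restarter share nor a restarter event rate, so what follows is illustration on assumed inputs. Let f be the share of matched comparator person-time from restarters, and h their hazard relative to other comparators that remains after matching. Assume SGLT-2i users have the same underlying hazard, λ, as the other comparators, and that the drug has no effect. The comparator rate is λ(1 − f + f·h), so the apparent hazard ratio is

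1 / (1 − f + f·h).

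| f | h = 0.8 | h = 1.25 | h = 1.5 | h = 2.0 |
|---|---|---|---|---|
| 10% | 1.02 | 0.98 | 0.95 | 0.91 |
| 20% | 1.04 | 0.95 | 0.91 | 0.83 |
| 30% | 1.06 | 0.93 | 0.87 | 0.77 |

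For example, f = 0.3 and h = 2.0 gives 1/1.3 = 0.77; f = 0.3 and h = 0.8 gives 1/0.94 = 1.06.

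**The case against.** The strongest reply is that the score already deals with this. Section 5.1.1 says that all observed variables that may affect treatment choice or outcome will be included, and names diabetes duration, severity, insulin use, add-on/switch status and lookback duration. Disease stage, the likeliest route to bias, is addressed there, and the insulin item bears on one of the older classes. The core covariate list sits in the full protocol (D1690R00015), which is not among these documents. This stands in part: a reader might infer that earlier treatment is left wholly unbalanced, and the text does not support that. But the named variables are proxies. Two patients with equal diabetes duration can differ in whether they once stopped the index class, and the add-on/switch indicator concerns the previous medication. Whatever the full list holds, Section 4.3 itself fixes the 12-month window for diabetes drugs.

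A second reply is that restarters may be the better comparators. Section 1.1 says SGLT-2i have mainly been recommended as third-line treatment in many countries, so their starters may resemble long-treated restarters more than first-time starters of an early-line drug. This also stands. It undercuts the assumption behind the table that SGLT-2i users share the hazard of non-restarters, and it argues against removing restarters from the primary cohort.

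Third, the larger shifts in the table need a residual hazard of 1.5 to 2.0 after matching on age, duration, severity, cardiovascular risk factors and health care use. Nothing in the documents supports or excludes that.

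**Conclusion.** The asymmetry is real. Restarters of older classes can enter as new comparators, SGLT-2i users are almost all first-ever users, and the 12-month diabetes-drug covariate cannot separate restarters from first-time starters. Earlier class use is handled only indirectly in the score as listed.

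Size and direction are unknown. Under the assumed ranges (f of 10% to 30%, h of 0.8 to 2.0) a null hazard ratio would read as about 0.77 to 1.06. The low end approaches the 20% reduction the study is designed to detect, but it is the extreme corner of the assumptions, and partial balancing by the proxies would shrink it.

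Three stronger readings are tempting and not supported:

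- That every SGLT-2i user is a first-ever user: Section 5.2.3 says otherwise for GP-based databases.
- That the washout creates this status: it comes from opening the study period at launch and indexing on the first prescription.
- That the plan is biased in favour of SGLT-2i: with h below 1 the shift goes the other way.

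The 970-event target is unaffected. This is an inexpensive improvement to the plan; it does not show that the planned comparison is invalid.

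**What to change.** Keep the one-year new-user rule for the primary cohort and make two changes.

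1. In Sections 4.3 and 5.1.1, measure prior use of each of the older diabetes classes over all available history before the index date, in the same way in both arms, and enter these indicators in the propensity score alongside lookback duration. An SGLT-2i user can have earlier sulfonylurea or insulin use just as a comparator can, so these terms can be balanced.
2. Add a sensitivity analysis limited to comparators with no recorded prior use of their index class. It would also yield the restarter share in each database, the figure now missing.

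Do not enter an indicator for ever having used the patient's own index class in the score, and do not match exactly on it. It is almost always zero in the SGLT-2i arm, so it would simply drop restarters while appearing to retain the one-year rule. Extending the washout itself to all available history is a debatable trade-off: the meaning of new user would then vary by patient and database, and comparators who may resemble SGLT-2i starters would be lost.

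The cost is modest. The work uses data already held: Section 3.2 sets no 12-month limit on the look-back for cardiovascular history, and lookback duration is already a candidate score variable. The documents do not say how far back prescription records reach in each database. Lookback varies, so short histories allow only a partial correction, and the sensitivity analysis will have fewer comparators.

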3.5 Participant Follow-up

Participants will be followed from the index date (excluding) until end of use of the index treatment or migration/leaving the practice/leaving the database, last date of data collection, death date (Sweden, Denmark, Norway, UK) or date of outcome.

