An as-treated approach will be used for the primary analysis to account for additions or switches to the index assigned treatment. A grace period of the duration of last issued prescription will be applied. As a sensitivity analysis, an intent-to-treat approach will also be applied in which subjects will be analyzed according to the treatment they were originally assigned to, regardless of whether there were any subsequent treatment changes. Further details regarding both these approaches, including the censoring rules, potentially allowing for time varying factors and imputation of missing data, will be provided in the SAP.

Meta-analysis

A meta-analysis approach, based on the DerSimonian and Laird method [6], will be used where the hazard ratio point estimates for each country are pooled together to obtain an overall summary weighted point estimate. In this approach, random-effects models with inverse variance weighting for each country will be implemented. Up to a 1:3 treatment allocation ratio of SGLT-2i to control patients will be applied to ensure that there are enough SGLT-2i patients for analysis.

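### The as-treated follow-up rule uses inconsistent end-of-use terms and lists no event that ends comparator time when an SGLT-2i is added

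*Combined protocol and SAP*

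**What the plan says.** **End of follow-up.** Section 3.1 reads "Patients will be followed from index date (excluding) to the earliest of end of use of the index medication group", followed by leaving the database, last data collection, death and outcome. The label is attached a few lines above, to the first "prescription of the SGLT-2i and other GLD (index medication group) during the study period". Section 3.2 words the same label slightly differently: "prescription of the SGLT-2i and other GLD classes (index medication group) during the study period".

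**What the comparator group contains.** Section 3.2: "The other GLD comparator group will include all diabetes medicines, allowing combinations and monotherapy use with the exception of SGLT-2i". Section 4.1: "The group other diabetes medications include all diabetes medications in A10A and A10B except SGLT-2 inhibitors".

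**Other terms for the same thing.** Section 3.5 follows patients "until end of use of the index treatment or migration/leaving the practice/leaving the database". Section 4.1 defines exposure by an index therapy and censors when no refill occurs within a grace period. Section 5.1.1 sets person-time to an index exposure episode that runs to the last day of follow-up.

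**Comparator index date.** It is tied to the start of one class. If a patient starts several, "one of the episodes will be randomly selected and the first day of that episode will be the index date for that patient" (3.1, repeated in 3.2).

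**Primary analysis.** Section 5.1.1: "An as-treated approach will be used for the primary analysis to account for additions or switches to the index assigned treatment". An intent-to-treat analysis that ignores later treatment changes is the sensitivity analysis. Further detail on both, including the censoring rules, is left to the SAP.

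**The concern.** The primary hazard ratio depends on when comparator person-time stops, and the text supports two different answers. Read at group level, a comparator who starts a class on top of metformin and then stops that class is still followed while on metformin. An SGLT-2i user on metformin who stops the SGLT-2i is censored. That sets time on the drug against time on any drug. Read at class level, both patients are censored.

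Under either reading, no listed event removes SGLT-2i time from the control arm when the drug is added to continuing index treatment. Such crossover is plausible: Section 1.1 says SGLT-2i were mainly recommended as third-line treatment, so patients starting other classes may later reach them, and Section 5.2.3 expects that comparators may have longer follow-up.

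Separate teams will build the exposure episodes (6.1.1), and their hazard ratios then enter one meta-analysis. If they read the text differently, the pooled estimate mixes different contrasts. The intent-to-treat sensitivity analysis would not expose the problem, because it keeps crossover time by design.

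**Working it through.** **Step 1. Apply the listed rules to four cases.**

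| Patient | Group level (3.1) | Class level (a possible reading of 3.5, 4.1, 5.1.1) |
|---|---|---|
| SGLT-2i user on metformin stops the SGLT-2i | ends | ends |
| Comparator on metformin stops the initiated class | continues | ends |
| Comparator switches to another non-SGLT-2i class | continues | ends |
| Comparator keeps the index drug and adds an SGLT-2i | continues | continues |

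Rows two and three show the inconsistency. Row four shows the gap, which does not depend on the reading. Adding an SGLT-2i ends neither the index group, treatment, therapy nor refill sequence, and it is not a named end event in 3.1, 3.5 or 4.1. The person-time definition in 5.1.1 does not close the gap, because it refers back to the last day of follow-up.

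**Step 2. Entry.** Sections 3.1 and 3.2 bar prior-year use of *that medicine class*. In 3.1 this means the class being started. In 3.2 the phrase follows a sentence defining the SGLT-2i class, so it could mean SGLT-2i. The inclusion and exclusion lists add no SGLT-2i lookback for comparators. The text can be read either way.

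**Step 3. Reproduce the plan's figures.** Inputs from Section 5.3: HR 0.80, two-sided alpha 0.05, power 85%, allocation 1:3 (SGLT-2i share 0.25), 970 events, rates of 0.5 and 0.625 per 100 person-years.

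- Events (Schoenfeld): (1.960 + 1.036)² / [0.25 × 0.75 × (ln 0.80)²] = 962, against 970 stated.
- Power at 970 events: Φ(√(970 × 0.1875) × 0.2231 − 1.960) = Φ(1.049) = 85.3%.
- Person-years: 970 / (0.005 + 3 × 0.00625) = 40,842 for SGLT-2i, and three times that is 122,526 for control. Both match.

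The plan's sample size is therefore not in dispute.

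**Step 4. Size of the dilution.** The documents give no crossover rate. Assume that a share f of comparator person-time is SGLT-2i exposed and carries the SGLT-2i rate.

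- Comparator rate = 0.625(1 − f) + 0.5f
- Observed HR = 0.5 / comparator rate
- Power = Φ(√(970 × 0.1875) × |ln HR| − 1.960)

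| f (assumed) | Comparator rate per 100 person-years | Observed HR | Power at 970 events | Events for 85% power |
|---|---|---|---|---|
| 0 | 0.6250 | 0.800 | 85.3% | 962 |
| 5% | 0.6188 | 0.808 | 82.0% | 1,055 |
| 10% | 0.6125 | 0.816 | 78.1% | 1,163 |
| 20% | 0.6000 | 0.833 | 69.1% | 1,441 |

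**The case against.** The strongest reply is that the group-level phrase in 3.1 is not the settled rule. The comparator index date is set by one class-level episode, 3.2 attaches the label to other GLD *classes*, and 3.5, 4.1 and 5.1.1 use terms that can mean the initiated class. Section 5.1.1 contrasts the as-treated analysis with an intent-to-treat one that ignores treatment changes, which implies that changes do matter to primary follow-up. It also defers the censoring rules to the SAP.

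Much of this stands. A reader might infer that comparator time definitely runs until all non-SGLT-2i treatment ends. The documents do not support that; they support only that the wording is inconsistent. A reader might also infer that a current SGLT-2i user qualifies as a comparator. Section 3.2 leaves that open.

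Following each arm while it remains on its group is also a recognisable choice, since the objective in 2.1 compares SGLT-2i with other GLD as a group.

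The reply does not close the add-on gap. Section 3.1 gives a closed list of which the earliest event applies, and SGLT-2i initiation is absent from it on every reading. The aim in 5.1.1 supplies no rule and conflicts with that list. The text here is already specific enough to be programmed, and programming it as listed leaves SGLT-2i time in the control arm.

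**Conclusion.** The point holds as a matter of inconsistent and incomplete wording in the rule that defines primary person-time. The end-of-use term changes between sections, and as listed the rule does not censor a comparator who adds an SGLT-2i to a continuing index drug.

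The resulting bias is toward the null. With 5% to 20% of comparator time exposed, a true hazard ratio of 0.80 would appear as 0.81 to 0.83, and power at 970 events would be 82% to 69% instead of 85%. These figures rest on three assumptions: the shares themselves, crossover time carrying the SGLT-2i event rate, and no selection in who crosses over. They illustrate the size and do not estimate what occurs in these databases. The effect of different stopping rules in the two arms was not quantified.

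**What to change.** 1. In 3.1, 3.5 and 4.1, add first SGLT-2i prescription as a censoring event for comparators in the as-treated analysis. Person-time and events before that date stay in the comparator arm.
2. In the entry criteria, require no SGLT-2i prescription on the comparator index date or in the 365 days before it.
3. Reconcile 3.1, 3.2, 3.5, 4.1 and 5.1.1 so that one end-of-use definition applies in every database. It may be the initiated class or the whole group, but the plan must say which, and must say what happens when a comparator stops the initiated class or switches within other GLD.

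The cost is wording in these sections and re-running the exposure episodes. Comparator follow-up will be somewhat shorter and comparator events fewer, so progress toward 970 events should be rechecked under the final rule. The intent-to-treat sensitivity analysis can stay as planned.
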